### 5.1 Inclusion Criteria

Participants are eligible to be included in the study only if all of the following criteria apply:

1. Have a histologically- or cytologically-documented, locally-advanced or metastatic solid tumor by pathology report and have received, or been intolerant to, all treatment known to confer clinical benefit.
2. Provide an archival or newly obtained tumor tissue sample and blood samples for assessment of RAS/RAF mutation and for biomarker analysis.
3. Have at least 1 measurable lesion as defined by RECIST 1.1 on imaging studies (computed tomography [CT] or magnetic resonance imaging [MRI]) as assessed by the investigator/local radiology review. Cutaneous lesions and other superficial lesions that are detectable only by physical examination and subcutaneous lesions detectable by CT are not considered measurable lesions for the purposes of this protocol, but may be considered as nontarget lesions.
4. Have a performance status of 0 or 1 on the Eastern Cooperative Oncology Group (ECOG) Performance Scale. (Obtain within 7 days prior to first dose of study treatment.)
5. Have the ability to swallow and retain oral medication.
6. Demonstrate adequate organ function as defined in [Table 3](#)

Note: All screening evaluations should be performed within the Screening period, and labs are to be obtained within 7 days of initiation of treatment.

Table 3 Adequate Organ Function Laboratory Values

System	Laboratory Value
Hematological	
Absolute neutrophil count	>1,500/mcL (>1,000/mcL)
Platelets	>100,000/mcL
Hemoglobin	>9 g/dL or >5.6 mmol/L a
Renal	
Serum creatinine or creatinine clearance (CrCl) (measured or calculated) b or Glomerular Filtration Rate (GFR) in place of CrCl	≤1.5 X ULN or ≥60 mL/min for participant with creatinine levels >1.5 X ULN
Hepatic	
Total bilirubin (serum)	≤1.5 X ULN or Direct bilirubin <ULN for participants with total bilirubin levels >1.5 X ULN
AST (SGOT) and ALT (SGPT)	<2.5 X ULN or ≤5 X ULN for participants with liver metastases
Coagulation	
International Normalized Ratio (INR) or Prothrombin Time (PT)	< 1.5 X ULN unless participant is receiving anticoagulant therapy
Activated Partial Thromboplastin Time (aPTT)	< 1.5 X ULN unless participant is receiving anticoagulant therapy

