### Medical Conditions

1. Have had chemotherapy, definitive radiation, or biological cancer therapy within 4 weeks (2 weeks for palliative radiation) prior to the first dose of study treatment, or has not recovered to CTCAE Grade 1 or better from any AEs that were due to cancer therapeutics administered more than 4 weeks earlier (this includes participants with previous immunomodulatory therapy with residual immune-related AEs). Participants receiving ongoing replacement hormone therapy for endocrine immune-related AEs will not be excluded from participation in this study.
2. Have a history of a second malignancy, unless potentially curative treatment has been completed with no evidence of malignancy for 2 years.

Note: The time requirement does not apply to participants who underwent successful definitive resection of basal cell carcinoma of the skin, superficial bladder cancer or in situ cervical cancer, or other in-situ cancers.

3. Have clinically active central nervous system metastases and/or carcinomatous meningitis. Participants with previously-treated brain or meningeal metastases may participate and be eligible for treatment provided they are stable and asymptomatic (without evidence of progression by MRI scan of the brain separated by at least 4 weeks after treatment), have no evidence of new or enlarging brain metastases, are evaluated within 4 weeks prior to first study treatment administration, and are off immunosuppressive doses of systemic steroids at least 2 weeks prior to enrollment

4. Have an active infection requiring therapy.

Note: Rescreening is possible after the infection resolves.

5. Have known human immunodeficiency virus (HIV) and/or Hepatitis B or C infections, or known to be positive for Hepatitis B antigen (HBsAg)/ Hepatitis B virus (HBV) DNA or Hepatitis C Antibody or RNA. Active Hepatitis C is defined by a known positive Hep C Ab result and known quantitative hepatitis C virus RNA results greater than the lower limits of detection of the assay.

6. Have undergone major surgery and has not fully recovered from any effects of major surgery without significant detectable infection and/or toxicity.

Note: Surgeries that required general anesthesia must be completed at least 2 weeks before first study intervention administration.

Note: Surgery requiring regional/epidural anesthesia must be completed at least 72 hours before first study intervention administration and participants should be recovered.

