#### **Prior/Concomitant Therapy**

15. Received prior therapy with a MEK inhibitor (eg, cobimetinib, trametinib), or an ERK inhibitor (eg, MK-8353, GCD-0994, ulixertinib), or a BRAF inhibitor (eg, dabrafenib, vemurafenib).
16. Received any herbal medications/supplements or any medications or foods that are strong or moderate inhibitors or inducers of CYP2C19 and CYP3A4 enzymes within 14 days prior to the start of study treatment ([Table 5](#)).

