8. Compounds with a narrow therapeutic index that are substrates for CYP3A4, -2C8, OATP1B1/3, and OCT2 should be avoided (Table 5). Once study treatment is initiated, the participant must not take medications listed in Table 5 during the course of the study.
- Table 5 is not a comprehensive listing. The investigator must use his/her medical judgment when a participant presents with a medication not on the list or call the Sponsor for clarification as needed. The investigator should consult an actively updated list of drugs that are clinically relevant inducers, or inhibitors of CYP450, including CYP2C19 and CYP3A4, and a narrow therapeutic index that are substrates for CYP3A4, -2C8, OATP1B1/3, and OCT2, as well as the product labeling of these compounds for reference.

Table 5 Examples of CYP3A4 Inducers/Inhibitors and Narrow Therapeutic Index Substrates of CYP3A4, CYP2C8, OATP1B1/3 and OCT2 Prohibited During the Trial

Strong CYP3A4 Inhibitorsa,g	Strong CYP3A4 Inducersb,g	Moderate CYP3A4 Inhibitorsc,g	Moderate CYP3A4 Inducersd,g
Atazanavir Cannabis (oral, IV) Clarithromycin Cobicistat Conivaptan Danoprevir and ritonavir Dasabuvir Elvitegravir and ritonavir Grapefruit juice and other juices f Idelalisib Indinavir and ritonavir Itraconazole Ketoconazole Lopinavir and ritonavir Paritaprevir and ritonavir (ombitasvir and/or dasabuvir) Posaconazole Nefazodone Nelfinavir Ritonavir Saquinavir and ritonavir Telithromycin Tipranavir and ritonavir Troleandomycin Voriconazole	Carbamazepine Enzalutamide Mitotane Phenobarbital Phenytoin Rifabutin Rifampin St John's wort e	Amprenavir Aprepitant Cimetidine Ciprofloxacin Clotrimazole Crizotinib Cyclosporine Diltiazem Dronedarone Erythromycin Fluconazole Fluvoxamine Fosamprenavir Imatinib Tofisopam Verapamil Grapefruit juice and other juices f	Bosentan Efavirenz Etravirine Modafinil
CYP3A4 Substrates with Narrow Therapeutic Index h	CYP2C8 Substrates with Narrow Therapeutic Index h	OATP1B1/1B3 Substrates with Narrow Therapeutic Index i	OCT2 Substrates with Narrow Therapeutic Index i

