## 6.6.2 Definition of Dose limiting Toxicity

All toxicities will be graded using NCI CTCAE v4.0 based on the investigator assessment.

The DLT window of observation will be during Cycle 1. The observation window can be modified to encompass Cycle 1 and 2 (and/or additional cycles).

The occurrence of any of the following toxicities during Cycle 1 will be considered a DLT, if assessed by the investigator to be possibly, probably, or definitely related to study treatment administration.

1. Grade 4 nonhematologic toxicity (not laboratory).
2. Grade 4 hematologic toxicity lasting  $\geq 7$  days, except thrombocytopenia:
  - Grade 4 thrombocytopenia of any duration
  - Grade 3 thrombocytopenia associated with clinically significant bleeding
3. Any nonhematologic AE  $\geq$  Grade 3 in severity should be considered a DLT, with the following exceptions: Grade 3 fatigue lasting  $\leq 3$  days; Grade 3 diarrhea, nausea, or vomiting without use of anti-emetics or anti-diarrheals per SOC lasting  $< 72$  hours; Grade 3 rash without use of corticosteroids or anti-inflammatory agents per SOC.
4. Any Grade 3 or Grade 4 non-hematologic laboratory value if:
  - Clinically significant medical intervention is required to treat the subject, or
  - The abnormality leads to hospitalization, or
  - The abnormality persists for  $\geq 72$  hours.
  - The abnormality is consistent with drug-induced liver injury and meeting the protocol Events of Clinical Interest criteria (see Section 8.4.7)

Exceptions: Clinically nonsignificant, treatable, or reversible laboratory abnormalities including liver function tests, uric acid, etc.

5. Febrile neutropenia Grade 3 or Grade 4:
  - Grade 3 is defined as absolute neutrophil count (ANC) <1000/mm^3 with a single temperature of >38.3 degrees C (101 degrees F) or a sustained temperature of ≥38 degrees C (100.4 degrees F) for more than 1 hour
  - Grade 4 is defined as ANC <1000/mm^3 with a single temperature of >38.3 degrees C (101 degrees F) or a sustained temperature of ≥38 degrees C (100.4 degrees F) for more than 1 hour, with life-threatening consequences and urgent intervention indicated.
6. An elevated AST or ALT laboratory value that is ≥3X the ULN and an elevated total bilirubin laboratory value that is ≥2X the ULN and, at the same time, an alkaline phosphate laboratory value that is <2X the ULN, as determined by the way of protocol-specified laboratory testing or unscheduled laboratory testing.

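### Exclusion criterion 1 limits toxicity recovery to treatment given more than 4 weeks before, so unresolved toxicity from more recent treatment can enter Cycle 1 and reach the DLT count

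*Combined protocol and SAP*

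**What the plan says.** Section 5.2, exclusion criterion 1, has two parts.

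- **Washout.** It excludes people who "Have had chemotherapy, definitive radiation, or biological cancer therapy within 4 weeks (2 weeks for palliative radiation) prior to the first dose of study treatment". Small-molecule targeted drugs and hormonal anticancer drugs are not named.
- **Recovery.** It excludes anyone not recovered to Grade 1 or better "from any AEs that were due to cancer therapeutics administered more than 4 weeks earlier".

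Other criteria reach some of the drugs not named. Criterion 15 bars any prior MEK, ERK or BRAF inhibitor. Criterion 16 bars "strong or moderate inhibitors or inducers of CYP2C19 and CYP3A4 enzymes within 14 days prior to the start of study treatment", and Table 5 (Section 6.5.2) gives examples that include anticancer drugs: "Carbamazepine Enzalutamide Mitotane Phenobarbital" among the strong inducers, and idelalisib, crizotinib and imatinib among the inhibitors. Criterion 17 sets 28 days for investigational agents.

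Inclusion criterion 1 (Section 5.1) selects people who "have received, or been intolerant to, all treatment known to confer clinical benefit", so recent anticancer treatment of any class is plausible at entry.

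Section 6.6.2 item 3 starts from the rule that any nonhematologic event of at least "Grade 3 in severity should be considered a DLT, with the following exceptions". The exceptions concern certain Grade 3 fatigue, diarrhea, nausea, vomiting and rash. Item 9 makes it a DLT to miss more than 25% of doses of either drug in Cycle 1 because of drug-related AEs. For any DLT, a rating of possibly related is enough.

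**The concern.** The recovery clause works only if every earlier treatment stopped at least 4 weeks before dosing. The same sentence breaks that premise by letting palliative radiation end 2 weeks before. A drug outside the washout list and outside criteria 15 to 17 has no stated interval, so its toxicity also escapes the recovery clause when it was stopped recently.

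The residual toxicities that matter most are rash and diarrhea. Section 6.5.3.1 expects rash with these study drugs, and both events have their own dose-modification rows in Table 7. Section 6.6.2 has no rule for baseline grade. A toxicity brought in from earlier treatment that worsens in Cycle 1 could therefore be attributed to the combination. DLT incidence is a primary endpoint and drives every escalation decision, in cohorts that start at 3 to 6 participants. At stake are an escalation held back for the wrong reason, and participants who begin two investigational drugs with toxicity that has not settled.

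**Working it through.** **1. What each rule requires for recent treatment**

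| Prior treatment | Interval before first dose | Recovery to Grade 1 required? |
|---|---|---|
| Chemotherapy, definitive radiation, biological therapy | 4 weeks (criterion 1) | Yes, because the interval makes the clause apply |
| Palliative radiation | 2 weeks (criterion 1) | Not if given 2 to 4 weeks before |
| MEK, ERK or BRAF inhibitor | Excluded (criterion 15) | Not applicable |
| Strong or moderate CYP3A4/CYP2C19 modulator | 14 days (criterion 16) | Not if stopped 2 to 4 weeks before |
| Investigational agent | 28 days (criterion 17) | Effectively yes |
| Other targeted or hormonal drug | None stated | Not if stopped within 4 weeks |

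Table 3 limits laboratory carry-over, criterion 7 covers cardiac findings and criterion 10 eye findings. None requires recovery from treatment-related rash or diarrhea.

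**2. Routes from carry-over to a DLT**

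- *By grade.* The event worsens to Grade 3 outside the item 3 exceptions, or to Grade 4 (item 1). Section 10.3.1 treats worsening of a pre-existing condition as an AE.
- *By missed doses.* Table 7 interrupts dosing for Grade 2 rash that worsens or fails to improve at reassessment, and for complicated Grade 1-2 diarrhea. Cycle 1 has 3 × 4 = 12 dosing days. Losing one 4-day block is 4/12 = 33%, above the 25% limit in item 9.

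Both routes also need a judgment that the event is related to study treatment.

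**3. Sensitivity of Table 2**

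Table 2 was first reproduced from its stated settings: Beta(1,1) prior, 30% target and ε₁ = ε₂ = 0.03, which gives an equivalence interval of 0.27 to 0.33. DU was assigned when P(rate > 0.30 given the data) exceeds 0.95. That cut-off is an assumption, because the documents do not state it. All 114 cells agree.

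Effect of one extra DLT:

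- n = 3: 0/3 E becomes 1/3 S; 1/3 S becomes 2/3 D; 2/3 D becomes 3/3 DU. Every decision changes.
- n = 6: 1/6 E becomes 2/6 S, and 3/6 S becomes 4/6 DU. However, 0/6 to 1/6 stays E and 2/6 to 3/6 stays S.

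**4. Illustration of size (assumed risks)**

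Assume a base DLT risk of 0.15, with one of the first three participants at risk p because of carry-over.

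- P(0/3) = 0.85² × (1 − p)
- P(1/3) = 0.85² × p + 2 × 0.15 × 0.85 × (1 − p)
- P(D or DU) = 1 − P(0/3) − P(1/3)

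After 1/3 (Stay), Section 4.3.4 caps the addition at 3, and 1/6 is Escalate. If the added three are unaffected:

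- P(Escalate by n = 6) = P(0/3) + P(1/3) × 0.85³, where 0.85³ = 0.614

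| p | P(0/3) | P(1/3) | P(D or DU), n = 3 | P(Escalate by n = 6) |
|---|---|---|---|---|
| 0.15 (no carry-over) | 0.614 | 0.325 | 0.061 | 0.614 + 0.325 × 0.614 = 0.814 |
| 0.30 | 0.506 | 0.395 | 0.099 | 0.506 + 0.395 × 0.614 = 0.748 |
| 0.50 | 0.361 | 0.489 | 0.150 | 0.361 + 0.489 × 0.614 = 0.661 |

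If one of the added three is affected in the same way, the last column becomes 0.506 + 0.395 × 0.506 = 0.71 and 0.361 + 0.489 × 0.361 = 0.54.

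Other base risks, first look only: at 10%, P(0/3) falls from 0.729 to 0.567-0.405; at 20%, from 0.512 to 0.448-0.320.

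A second model spreads carry-over evenly, with counted rate 1 − (1 − true rate)(1 − q). For a true rate of 20% and an assumed q of 10%, the counted rate is 1 − 0.80 × 0.90 = 0.28. P(0/3) then falls from 0.512 to 0.72³ = 0.373. For a cohort of six, P(Escalate) falls from 0.655 to 0.464. The direction is the same.

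**The case against.** The best case for the plan has six parts.

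- **DLT exemptions.** Item 3 partly exempts the very events at issue: short Grade 3 fatigue; short Grade 3 diarrhea, nausea or vomiting, subject to a condition on supportive medication; and Grade 3 rash under a similar condition. This stands. A reader might infer that one further grade on a Grade 2 event is always a DLT. The text does not say that.
- **Other entry checks.** Inclusion 4 (ECOG 0 or 1), inclusion 5 (able to swallow and retain oral medication) and exclusion 12 (GI conditions affecting absorption, in the investigator's opinion) bear on fatigue, vomiting and some diarrhea. So these events are not wholly unscreened. None of the three asks for recovery to Grade 1, and none touches rash.
- **Attribution.** Section 10.3.4 asks whether another cause explains the event better, and Section 10.3.1 does not count a pre-existing condition that does not worsen. These lower the chance of a miscount. The threshold in Section 6.6.2 is still possibly related, for events expected with the study drugs, and some worsening would be a true drug effect.
- **Coverage.** Criteria 15 to 17 reach many drugs, Table 5 is not exhaustive, and chemotherapy is undefined, so a site may read it broadly. Section 6.5.2 also prohibits radiation during Screening. But Screening lasts up to 28 days and can be shorter, so radiation before consent can still fall 2 to 4 weeks before dosing, as criterion 1 expressly allows.
- **Hormonal drugs.** No passage links them to rash or diarrhea. They belong in the list for completeness; the argument about rash and diarrhea does not rest on them.
- **Size and direction.** The risks are assumed, the first look overstates the effect on the final decision, escalation also draws on PK, pharmacodynamic and safety review, and the error is on the cautious side. All of this stands.

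**Conclusion.** The gap in criterion 1 is real on the text. Recovery is not required for toxicity from palliative radiation 2 to 4 weeks before dosing, or from a recently stopped drug that criteria 1, 15 and 17 do not cover. Such toxicity can reach the DLT count, but only if it worsens outside the exemptions or costs more than a quarter of the doses, and is judged at least possibly related.

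Two stronger readings are not supported. One is that targeted and hormonal drugs have no washout anywhere in the protocol; criteria 15 to 17 cover part of them. The other is that carry-over cuts the chance of escalation from 61% to as low as 36%. That is a first-look figure under an assumed 50% risk in one of three participants; by six participants the same assumption gives 66% against 81%. The documents supply no carry-over rate, so neither figure is an estimate for this trial.

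The bias runs toward under-escalation and a preliminary RP2D that may be set too low. The point merits a wording change because it affects a primary endpoint and costs little. It does not invalidate the dose-finding rules.

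**What to change.** Amend exclusion criterion 1 in two places.

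1. Delete the last six words of "from any AEs that were due to cancer therapeutics administered more than 4 weeks earlier", so that recovery to Grade 1 or better applies to AEs from all prior anticancer treatment, including palliative radiation given 2 to 4 weeks before the first dose.
2. Reword the washout list "Have had chemotherapy, definitive radiation, or biological cancer therapy within 4 weeks (2 weeks for palliative radiation" so that it covers any systemic anticancer therapy (chemotherapy, small-molecule targeted, hormonal or biological) as well as definitive radiation. The sponsor should state the window for the added classes.

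No sample size and no Table 2 entry changes. The cost is a short amendment and a longer wait before first dose for some participants; the documents do not show how many.

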#### **Prior/Concomitant Therapy**

15. Received prior therapy with a MEK inhibitor (eg, cobimetinib, trametinib), or an ERK inhibitor (eg, MK-8353, GCD-0994, ulixertinib), or a BRAF inhibitor (eg, dabrafenib, vemurafenib).
16. Received any herbal medications/supplements or any medications or foods that are strong or moderate inhibitors or inducers of CYP2C19 and CYP3A4 enzymes within 14 days prior to the start of study treatment ([Table 5](#)).

#### **Prior/Concurrent Clinical Study Experience**

17. Is currently participating and receiving study treatment in a study of an investigational agent or has participated and received study treatment in a study of an investigational agent or has used an investigational device within 28 days of administration of selumetinib.

Note: Participants who have entered the Post-treatment Follow-up Phase of an investigational study may participate as long as it has been 4 weeks since the last dose of the previous investigational agent.

## Diagnostic Assessments

### Other Exclusions

18. Have a history of allergic reactions attributed to compounds of similar chemical or biologic composition to agents and/or excipients used in the study.

### Pregnancy Exclusion

19. A WOCBP who has a positive urine pregnancy test within 24 hours before the first dose of study treatment (see Appendix 5). If the urine test cannot be confirmed as negative, a serum pregnancy test is required. In such cases, the participant must be excluded from participation if the serum pregnancy result is positive.

## 5.3 Special Considerations for Subjects of Asian Ethnicity

Plasma exposure of selumetinib ( $C_{max}$  and AUC) is higher, at a population level, in subjects of Asian ethnicity by approximately 1.5- to 2-fold, compared with Western subjects. However, the PK of selumetinib show considerable variation and there is overlap in the range of exposure experienced by Asian and Western subjects (some individual Asian subjects have similar plasma levels to those in Western subjects). The higher average plasma exposure was not associated with a change in the tolerability profile of single dose selumetinib.

Patients of Asian ethnicity are not excluded from studies evaluating selumetinib. However, when considering enrolling an individual of Asian ethnicity to a selumetinib clinical study, investigators should make a clinical judgment as to whether the potential risk of experiencing higher selumetinib plasma levels outweighs the potential benefit of treatment with selumetinib. Investigators should be aware of the potentially higher risk of adverse events when monitoring patients of Asian ethnicity receiving treatment in clinical studies of selumetinib.

Additional details are available in the selumetinib IB.

## 5.4 Lifestyle Considerations

### 5.4.1 Meals and Dietary Restrictions

Selumetinib should be taken on an empty stomach; no food or drink other than water for approximately 2 hours prior to dosing and approximately 1 hour after dosing. The participant must be fasting for the glucose (finger stick) obtained pre-dose on C2D4 visit.

Foods that contain CYP3A inhibitors must not be consumed during the study. Grapefruit juice and other fruit juices are known to be CYP3A inhibitors, and should not be consumed for 2 weeks before the first dose of MK-8353 and for the entire duration of the study. Consumption of CYP3A4 inhibitors, such as grapefruit juice, may significantly increase the levels of MK-8353 and cause increased toxicity.

St. John's Wort is a CYP3A inducer, and the consumption of St. John's Wort or products containing St. John's Wort may reduce the levels of MK-8353.

#### **5.4.2 Caffeine, Alcohol, and Tobacco Restrictions**

There are no study specific restrictions.

#### **5.4.3 Activity Restrictions**

There are no study specific restrictions.

### **5.5 Screen Failures**

Screen failures are defined as participants who consent to participate in the clinical study, but are not subsequently entered in the study. A minimal set of screen failure information is required to ensure transparent reporting of screen failure participants to meet the Consolidated Standards of Reporting Trials (CONSORT) publishing requirements and to respond to queries from regulatory authorities. Minimal information includes demography, screen failure details, eligibility criteria, and any AEs or SAEs meeting reporting requirements as outlined in the data entry guidelines.

